1.2.3. Study Procedures

The schedule of assessments, as outlined in the study protocol, is provided in [Table 2](#).

Table 2 Schedule of Assessments

Study Procedure	Screening ¹ within 36 hours prior to Randomization	Days 1-10 During Hospitalization ²	Day 5 (5 Days After Randomization)	EOI ² IV-to-Oral Transition	EOT ³ Within 1 Day of Last Dose (IV or PO)	TOC (14-17 Days After Randomization & ≥ 3 days after last dose)	FU (21-28 Days After Randomization)
Informed Consent ¹	X						
Medical History/Height & Weight	X						
Signs and Symptoms	X	X	X	X	X	X	X
Physical Exam	X	X ⁴	X	X	X	X	X
Temperature	X	X ⁵	X	X	X	X	X
Resting Vital Signs ⁶	X	X	X	X	X	X	X
Prior/Concomitant Medications ⁷	X	X	← X →				
Hematology/Chemistry ⁸	X			X	X	X	X
Coagulation	X			X	X		X
Urinalysis ⁹	X		X	X	X	X	X
Calculated Creatinine Clearance	X	X ¹⁰	X	X as clinically indicated			
Serum Pregnancy Test ¹¹	X					X	
Blood Cultures	X	X ¹²	← X ¹² →				
Urine Cultures ¹³	X		X	X	X	X	X
Adverse Events ¹⁴	X	X	← X →				
Clinical Outcome Assessment			X	X	X	X	X
Study Drug Administration ¹⁵		X	X	X			
Length of Treatment Determination ¹⁶			X				
Verify PO Study Drug Compliance					X		
Plasma PK Assessments ¹⁷		X	X				

See footnotes below and on following page.

Key: B/P = blood pressure; CFU = colony-forming unit; cUTI = complicated urinary tract infection; eCRF = electronic case report form; EOI = End of IV visit; EOT = End of Treatment visit; FU = Follow-up visit; HR = heart rate; IV = intravenous; PK = pharmacokinetic; PO = oral; RBC = red blood cell; RR = respiration rate; TOC = Test of Cure visit; WBC = white blood cell.

1. If Dose 1 and Screening occur on the same day then the signs and symptoms, physical exam, temperature, resting vital signs, and hematology/chemistry do not need to be repeated. Procedures performed as standard of care within 36 hours prior to randomization may be used to determine eligibility. Informed consent must be obtained prior to performing any study specific procedures that are not standard of care. However, urine and blood specimens collected during routine care prior to subject consent may be used for study purposes. If routine care results are used to determine eligibility, central laboratory blood tests must still be performed.
2. If EOI occurs on the same day as a dosing day during hospitalization then the visit should be completed as an EOI visit.
3. EOT assessments are to be performed at premature withdrawal or treatment failure and within 24-h of last dose. If EOT occurs on the same day as a dosing day during hospitalization then the visit should be completed as an EOT visit.
4. A symptom directed Physical Exam should be conducted daily while in hospital. Complete physical exams should be performed at Screening, Day 5, EOI, EOT, TOC and FU visits.
5. Temperature (oral, rectal, tympanic, or by temporal artery) should be assessed per institution guidelines while in hospital, and the highest daily value recorded in the eCRF.
6. RR, HR, B/P at: (i) Screening, (ii) daily while in hospital, (iii) Day 5, (iv) EOI, (v) EOT, (vi) TOC, and (vii) FU.
7. At screening visit, record all prior and concomitant medications, including all prescription, over-the-counter and herbal medications, taken within 1 week prior to randomization, including both day and time for all antibiotics administered in the 72-h prior to randomization. The following subjects who have received previous/ongoing antibiotics are eligible for enrollment: (a) subjects with suspected acute cUTI who have received a single dose of effective non-study antibiotics for the acute cUTI; (b) subjects who developed signs and symptoms of cUTI while on an antibiotic for another indication. No concomitant systemic antibacterials effective in cUTI are permitted after the initial dose of study drug through the FU visit, other than subjects on rescue/non-study antibacterial therapy. See Protocol Section 10.6 for prohibited concomitant medications.
8. Hematology and chemistry will be performed at: Screening, EOI, EOT, TOC, and FU.
9. Urine microscopy for RBC, WBC, crystals, and casts performed at: (i) Screening, (ii) Day 5, (iii) EOI, (iv) EOT, (v) TOC, and (vi) FU.
10. If creatinine clearance is <50 at Screening, creatinine clearance should be recalculated daily through Day 5 and thereafter as clinically indicated. Creatinine clearance should be calculated based upon local laboratory results in order to make timely dose adjustments, if needed; however, samples are also required to be sent to the central lab for assessment. Ertapenem/placebo and levofloxacin dosing should be increased or decreased according to the prescribing information.
11. If a local serum pregnancy test is not available or results cannot be received within 4 hours of sampling at the investigative site then a urine pregnancy test may be utilized locally to obtain timely results for randomization. All female subjects of childbearing potential will have a serum pregnancy test performed by the central laboratory.
12. Obtain a set of aerobic and a set of anaerobic samples from 2 separate venipuncture locations at Screening. Upon knowledge of a positive culture for a pathogen, blood cultures should be repeated until sterile (ie, both sets of cultures from 2 separate venipuncture sites are negative for pathogens) through the FU visit. Await results before drawing additional sets of blood cultures. If baseline cultures are negative, follow-up cultures should be obtained only if clinically indicated (eg, signs and symptoms of persistence, relapse, or new infection).
13. Collected from a mid-stream urine specimen, a newly-placed urinary catheter, cystoscopy, suprapubic aspiration, or a properly disinfected collection port.
Urine cultures should be processed using a calibrated loop to identify a quantitative count of bacteria at a lower limit of 103 CFU/mL. The colony count and pathogenic microorganism(s) identification will be recorded and the purified isolate(s) will be sent to the central laboratory where species confirmation and antimicrobial susceptibility testing will be performed.
14. Document any adverse events that occur from the signing of informed consent through study completion. Prior conditions should be documented as medical history
15. Expected treatment duration is 7 days unless clinical failure occurs earlier; maximum treatment duration is ten days (total IV and PO). The 24-h interval between IV doses can be shortened (but not prolonged) by up to 2-h (ie, interval of 22-h to 24-h) from the first dose during doses 1-3 to adapt to a normal hospital schedule. After the third dose, the permitted IV administration window is q24h ± 90 minutes. At a minimum, the first 5 IV doses must be administered in an in-patient hospital setting; subsequent doses may be administered on an out-patient basis. Contact Medical Monitor for dosing beyond 7 doses.
16. Subjects should receive 7-10 days of treatment. Specific criteria for determining length of treatment are described in Protocol Section 11.3.3.
17. Please refer to Protocol Section 24 for schedule of plasma PK sample collection on Day 1, Day 2, and Day 5.

2. DATA MANAGEMENT

Data management procedures, including database design, development of the data dictionary, and coding of medical history, adverse events (AEs) and medications, will be performed at a Contract Research Organization (CRO). Data will be entered into an electronic case report form (eCRF) at the study sites. A series of logic and consistency checks will be conducted to ensure accuracy and completeness of the clinical database. One or more analysis databases, including detailed documentation, will be developed to support the analyses described in this SAP. Safety lab results, microbiology data, and pharmacokinetic data will be electronically transmitted from central labs. After database lock, randomization data will be provided electronically from the IWRS vendor. Refer to the Data Management Plan for further Data Management details.

3. SUBJECT POPULATION

3.1. Population Definitions

The subject populations defined in this section will be evaluated and used for presentation and analysis of the data.

3.1.1. Intent-to-Treat (ITT) Population

The ITT analysis set will consist of all randomized subjects regardless of whether or not the subject received study drug.

3.1.2. Safety Population

The Safety analysis set will consist of all randomized subjects who receive any amount of study drug. All safety analyses will be conducted in this population and will be presented in the summary tables by the treatment the subject actually received. A subject randomized to the ertapenem arm who mistakenly receives eravacycline will be included in the eravacycline arm. A subject randomized to the eravacycline arm who mistakenly receives ertapenem will be included in the ertapenem arm if ertapenem is given for the entire course of IV therapy and will be included in the eravacycline arm if both ertapenem and eravacycline are received.

3.1.3. All Treated (MITT) Population

The MITT population will consist of all randomized subjects who receive any amount of study drug. Analyses in this population will be presented in summary tables by the treatment arm to which the subject was randomized.

3.1.4. Microbiological Intent-to-Treat (micro-ITT) Population

The micro-ITT population will consist of all subjects in the ITT population who have at least 1 baseline bacterial pathogen on culture of urine or blood that causes urinary tract infection against which eravacycline and ertapenem have expected antibacterial activity. As clinical breakpoints for eravacycline have not yet been determined, for the purpose of this analysis population, all baseline bacterial pathogens will be considered susceptible to eravacycline with the exception of *Pseudomonas* species. Analyses in this population will be presented in summary tables by the treatment arm to which the subject was randomized.

To be considered a baseline pathogen, both of the following must be met:

1. The organism must have been isolated from a suitable urine or blood specimen obtained between 36 hours prior to enrollment and the first dose of study drug). A suitable urine specimen is one collected from a clean-catch mid-stream urine specimen, a newly-placed urinary catheter (including urethral catheters, supra pubic catheters, and nephrostomy tubes), cystoscopy, supra pubic aspiration, or a properly disinfected collection port.
2. The baseline urine specimen must grow at least 1, but no more than 2 bacterial isolates at $\geq 10^5$ CFU/mL each (or at $\geq 10^4$ CFU/mL if obtained via suprapubic aspiration, new nephrostomy or cystoscopy). If more than 2 bacterial isolates are identified, the urine culture will be considered uninterpretable unless the specimen is obtained via suprapubic aspiration, nephrostomy tube newly placed or cystoscopy, 1 of the isolates comprises $\geq 80\%$ of the total growth (predominant), or 1 or more isolates are also isolated

simultaneously from a blood culture. In the second case, only the predominant organism will be considered a baseline pathogen. In the latter case, only organisms isolated simultaneously from the urine culture and the blood culture will be considered baseline pathogens.

All baseline urine cultures will be reviewed in a blinded manner by the Sponsor Microbiology Review Committee (MRC) for acceptability and final pathogen determination. The organism's identity as determined at the local laboratory will be verified by the central laboratory. If the Genus identification is the same between the local and central microbiology laboratory but the species identification is discrepant, the central laboratory identification will be used. If the local laboratory grows an acceptable pathogen but the central laboratory is not able to grow the isolate, if isolates were lost during transportation or storage, or there are major discrepancies between the local and central laboratory in the identification of species, the central laboratory will request that the local laboratory resend the isolate. If the central laboratory is still not able to identify the isolate for any reason, the local laboratory determination of Genus and species will be used for pathogen identification. Any remaining major discrepancies in species identification between the central and local laboratory will be reviewed by the Sponsor MRC in a blinded manner for final identification of the isolate.

There are 3 categories of pathogen identification as follows:

1. Always a pathogen:
 - *Escherichia coli*
 - *Klebsiella* spp.
 - *Proteus* spp.
 - *Citrobacter* spp.
 - *Enterobacter* spp.
 - *Serratia* spp.
 - *Providencia* spp.
 - *Morganella* spp.
 - Other Enterobacteriaceae
 - *Enterococcus* spp.
 - Beta-hemolytic streptococci including:
 - *Streptococcus agalactiae*
 - *Streptococcus pyogenes*
 - *Streptococcus bovis*
 - *Staphylococcus aureus*
 - *Staphylococcus saprophyticus*
 - *Acinetobacter* spp.

- *Corynebacterium urealyticum*
2. Not considered a pathogen:
- *Lactobacillus* spp.
 - *Corynebacterium* spp. (EXCEPT *Corynebacterium urealyticum*)
 - *Propionibacterium* spp.
 - Viridans group streptococci, including:
 - *Streptococcus oralis*
 - *Streptococcus mitis*
 - *Streptococcus salivarius*
 - *Streptococcus parasanguinis*
 - *Streptococcus milleri*
 - *Streptococcus constellatus*
 - *Streptococcus intermedius*
 - *Streptococcus anginosus*
 - *Streptococcus gordonii*
 - *Streptococcus sanguis*
 - *Streptococcus sanguinis*
 - *Streptococcus sobrinus*
 - *Streptococcus vestibularis*
 - *Streptococcus oralis*
 - *Streptococcus salivarius*
 - *Streptococcus mutans*
3. The following organisms will be considered pathogens if grown from urine culture at $\geq 10^5$ CFU/mL if obtained via a newly placed catheter or at $\geq 10^4$ CFU/mL if obtained via suprapubic aspiration, new nephrostomy or cystoscopy. They will not be considered pathogens when grown from urine culture if obtained via midstream clean catch or a disinfected collection port. They will also not be considered pathogens when grown from blood cultures, unless simultaneously grown from urine culture at $\geq 10^5$ CFU/mL if

obtained via a newly placed catheter or at $\geq 10^4$ CFU/mL if obtained via suprapubic aspiration, new nephrostomy or cystoscopy:

- Coagulase negative staphylococci, including:
 - *Staphylococcus epidermidis*
 - *Staphylococcus hominis*
 - *Staphylococcus haemolyticus*
 - *Staphylococcus simulans*
 - *Staphylococcus capitis*
 - *Staphylococcus warneri*
 - *Bacillus* spp. (other than *B. anthracis*)
4. The following organisms will be considered non-susceptible to eravacycline or comparator and will NOT be analyzed as pathogens:
- *Pseudomonas* spp.
 - Yeast and fungi
5. Pathogens for MRC review: isolates will be reviewed in a blinded manner by the MRC on a case-by-case basis if none of rules 1 through 3 above apply.

If more than 1 suitable urine culture specimen is obtained prior to the first dose of study drug therapy, and the same pathogen is isolated, the one with the highest MIC to study drug will be utilized in all analyses and the highest colony count will be used. If pathogens have the same MIC to study drug, the pathogens will be considered equivalent and a representative isolate will be selected from among them based on the lowest central laboratory accession number and the highest colony count will be used.

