µg/mL); and methicillin-resistant, *S. aureus* (n=493; 0.06/0.12 µg/mL).(5) Eravacycline had reduced activity against *P. aeruginosa* (n=499; 8/16 µg/mL). The same primary Gram-negative pathogens (i.e., *E. coli* and *K. pneumoniae*) isolated and identified in the complicated intra-abdominal infection (cIAI) phase 2 and phase 3 studies were also the major pathogens in the phase 3 cUTI study. Major Gram-positive pathogens (i.e., *E. faecalis* and *S. aureus*) were also in common between cIAI and cUTI studies. The full description of the *in vitro* antibacterial activity of eravacycline can be found in the Investigator's Brochure (IB).

The efficacy of eravacycline in sepsis, tissue, lung, and pyelonephritis/cUTI murine models of infection has been described by Murphy et.al (3). Eravacycline is effective in reducing the bacterial burden in kidneys from mice that have been infected with a tetracycline-resistant uropathogenic strain of *E. coli* or an extended-spectrum β-lactamase-producing strain of *K. pneumoniae*.

In terms of Gram-positive pathogens, eravacycline has activity against both nosocomial and community-acquired methicillin-susceptible or methicillin-resistant *Staphylococcus aureus* strains, vancomycin-susceptible or vancomycin-resistant *Enterococcus faecium*, and *Enterococcus faecalis*. In cUTIs, enterococci and streptococci can be frequently isolated, and eravacycline consistently exhibits excellent activity against these strains (10).

The high degree and reliability of *in vitro* antibacterial activity against multidrug-resistant Gram-negative pathogens, the efficacy observed with eravacycline in established animal models of infection, and the efficacy and tolerability established in phase 2 and phase 3 studies of cIAIs warrant clinical development of eravacycline as a single daily dose IV treatment option for cUTIs.

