14.2.2 Per Pathogen Microbiological Outcomes

Per pathogen microbiological outcome will be determined for the Day 5, EOI, EOT, TOC, and FU visits. Outcomes will be classified as success, failure, or indeterminate/missing based on the microbiologic response definitions (Section 11.1.7).

All purified bacterial pathogens cultured from clinical specimens will be evaluated for susceptibility to study drugs and the emergence of resistance and overgrowth of non-susceptible organisms.

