3.2.2. Process for Determining Inclusion in Analysis Populations

Inclusion into the ITT and Safety populations will be determined programmatically from the eCRF data. Inclusion into the CE populations will be determined programmatically from the eCRF data and the manual review conducted by the ERC.

Inclusion into the micro-ITT population will be determined programmatically by incorporating the outcome of the review of the isolates by the MRC. The MRC will determine whether each

isolate (baseline and post-baseline) is considered a pathogen based on a review of information regarding baseline samples such as method of collection of the specimen, CFU/mL, local and central genus and species identification. Inclusion into the ME and micro-MITT populations will be determined programmatically.

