5.7.3.5. Microbiological Outcomes

Microbiologic response by baseline pathogen will be determined as the proportion of subjects with a microbiological success at the EOI (micro-ITT and ME-EOI populations) and TOC (micro-ITT and ME-TOC populations) visits for each pathogen isolated at baseline. Microbiologic response for levofloxacin resistant and ertapenem resistant baseline pathogens will also be presented.

For subjects with baseline pathogens obtained from blood culture (ie, for bacteremic subjects), microbiologic success by baseline pathogen will also be summarized separately for the micro-ITT population.

In addition, a table will list all subjects in each treatment group with at least 1 baseline pathogen obtained from blood culture, including the per subject clinical response, per subject microbiological response, and the per-pathogen microbiological response for each pathogen.

Per-pathogen microbiological success will also be summarized by baseline pathogen and MIC to study drug received for those pathogens with a sample size of at least 10 in 1 of the treatment groups in the micro-ITT population.

Microbiological categories for pathogens identified after baseline assessment are superinfection and new infection, which are defined as follows:

- Superinfection: Emergence of a new pathogen during therapy, from urine or blood cultures, with emergence or worsening of signs and symptoms of infection (ie, is determined by the Investigator to be a clinical failure)
- New infection: Emergence of a new pathogen after completion of therapy, from urine or blood cultures, with emergence or worsening of signs and symptoms of infection (ie, is determined by the Investigator to be a clinical failure)

The number and percentage of subjects with a superinfection or new infection after baseline will be presented by treatment group. A listing will be provided that presents the subjects with a superinfection and new infection including the type of specimen and pathogen.

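### SAP 3.1.4 item 4 bars Pseudomonas and yeast/fungi as pathogens without limiting this to baseline, and the SAP has no analysis of new organisms without clinical failure

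*SAP*

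**What the plan says.** - **Organism rules.** SAP 3.1.4 sorts organisms into lists. List 1 is always a pathogen, list 2 never is, and list 3 depends on how the specimen was taken. Item 4 covers *Pseudomonas* species, yeast and fungi: "The following organisms will be considered non-susceptible to eravacycline or comparator and will NOT be analyzed as pathogens". Item 5 sends isolates to the MRC "on a case-by-case basis if none of rules 1 through 3 above apply"; it does not mention rule 4.
- **Who applies them.** SAP 3.2.2 says the MRC decides whether each "isolate (baseline and post-baseline) is considered a pathogen based on a review of information regarding baseline samples".
- **Where new organisms are summarised.** SAP 5.7.3.5 defines two categories: "Superinfection: Emergence of a new pathogen during therapy, from urine or blood cultures, with emergence or worsening of signs and symptoms of infection" and "New infection: Emergence of a new pathogen after completion of therapy, from urine or blood cultures, with emergence or worsening of signs and symptoms". Both add that the investigator must have judged the subject a clinical failure. The table and the listing show these two categories only.
- **What the protocol commits to.** Protocol 14.2.2, and the Microbiology paragraph of the synopsis, say cultured bacterial pathogens will be evaluated for susceptibility and for "emergence of resistance and overgrowth of non-susceptible organisms". Neither place adds a clinical-failure condition.
- **The known gap in activity.** Protocol 7.2: "Eravacycline had reduced activity against" *P. aeruginosa*, with MIC50/90 of 8/16 µg/mL. Protocol 7.4 names the same organism as the one exception to steady-state urine levels exceeding the MIC90.

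**The concern.** Leaving out non-susceptible organisms is sensible when deciding who enters the micro-ITT population. It does not suit a superinfection table, because organisms that the study drug does not cover are the ones expected to emerge under treatment. If item 4 also governs post-baseline isolates, the organism that the protocol itself names as eravacycline's gap drops out of the only table of emergent organisms, while list 1 organisms such as *Enterococcus* stay in.

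The second issue does not depend on how item 4 is read. The clinical-failure condition leaves overgrowth without symptoms out of every planned summary, for any organism. SAP 1.1.1 says differences from the protocol's planned analyses will be outlined, and SAP section 6 records none. At stake is the descriptive reporting of a recognised harm of broad-spectrum antibiotics.

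**Working it through.** The plan gives no figure to reproduce, so the check traces cases through the definitions.

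**Step 1: rules that could pick up a new organism.**

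- Microbiological response (SAP 5.7.1) refers to the baseline pathogen only.
- Decreasing susceptibility (SAP 5.7.3.5) requires that the baseline pathogen persists.
- Superinfection and new infection (SAP 5.7.3.5) require a new pathogen and clinical failure.

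**Step 2: four cases.** In each, the baseline *E. coli* falls below 10^4 CFU/mL and one new organism grows in urine at 10^5 CFU/mL or more during therapy.

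| New organism | Clinical response | Responder outcome (SAP Table 5) | In superinfection table? |
|---|---|---|---|
| *Enterococcus* (list 1) | Failure | Non-responder | Yes |
| *Pseudomonas* (item 4) | Failure | Non-responder | No on the plain reading; yes or MRC judgement on other readings |
| *Enterococcus* (list 1) | Cure | Responder | No |
| *Pseudomonas* (item 4) | Cure | Responder | No |

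The last two rows follow from SAP 5.7.3.5 alone and need no inference. Row 2 depends on the scope of item 4.

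**Step 3: scope of item 4.** Three things point to it reaching post-baseline isolates: item 4 does not contain the word baseline, SAP 3.2.2 gives the MRC post-baseline isolates to judge, and the SAP has no second organism list. Two things point the other way. The section defines a baseline population: "for the purpose of this analysis population, all baseline bacterial pathogens will be considered susceptible to eravacycline with the exception of" *Pseudomonas* species. And item 5, read literally, would send *Pseudomonas* to case-by-case review because rule 4 is not among the rules it names. SAP 3.1.4 also announces three categories and then lists five. Two programmers could build different tables from this text.

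**Step 4: is the gap real on the protocol's own figures?** Ratio = urine concentration / MIC, from Protocol 7.4 and 7.2.

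- Steady-state trough: 9.19 / 8 = 1.15 times the MIC50; 9.19 / 16 = 0.57 times the MIC90.
- First dose, 0 to 8 h: 6.92 / 16 = 0.43 times the MIC90.
- First dose, next 16 h: 2.83 / 16 = 0.18 times the MIC90.

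This agrees with the exception that the protocol states.

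**Step 5: illustration of size.** The documents give no rate of emergence. Assume that 1% to 5% of the 395 micro-ITT subjects planned per arm grow new *Pseudomonas*, and that 10% to 50% of those also fail clinically.

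- Subjects with new growth: 395 × 0.01 = 4.0 to 395 × 0.05 = 19.8 per arm.
- Left in the table by the clinical-failure condition alone: 4.0 × 0.10 = 0.4 to 19.8 × 0.50 = 9.9 per arm.
- Left once item 4 is applied as well: 0.

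The two filters remove different quantities. Item 4 removes at most the symptomatic cases (0.4 to 9.9); the clinical-failure condition removes the rest.

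**The case against.** The strongest counter-argument is that item 4 belongs to the micro-ITT definition. Its reach to post-baseline isolates rests on one parenthesis in SAP 3.2.2, in a sentence that goes on to speak of baseline samples, and SAP 5.7.3.5 does not refer back to 3.1.4. SAP 3.2.1 places pathogen determination under the Microbiological Outcomes Review Plan, which was not available and may set its own post-baseline rule. This stands as a limit on certainty. A reader might infer that the table must show zero *Pseudomonas*; the documents make that likely, not certain.

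A reader might also infer that the comparison is tilted toward eravacycline. That is not supported. Item 4 applies to both arms and is worded for eravacycline or comparator. The documents give no ertapenem activity data for *Pseudomonas*, *Enterococcus* or *Acinetobacter*. After the IV phase, both arms generally receive the same oral drug.

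Three further points stand in part:

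- The protocol's commitment concerns bacterial pathogens, so it does not extend to yeast, and it does not specify a table by arm.
- Symptomatic cases are still clinical failures, reasons for non-response are summarised by arm (SAP 5.7.1.1), and collected data go into by-patient listings (SAP 4.8). None of these is a summary of emergent organisms.
- Requiring clinical failure separates infection from colonisation. That is a fair definition of superinfection, but it does not answer a commitment to evaluate overgrowth.

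Exclusion criteria 7 and 10 in Protocol 10.2 lower the baseline risk of fungal and *Pseudomonas* infection. They do not rule out emergence on treatment.

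**Conclusion.** The point holds in two parts. First, SAP 3.1.4 item 4 is not limited to baseline and conflicts with item 5; on the plain reading, symptomatic new *Pseudomonas* would not enter the superinfection/new-infection table or listing. This assumes that the unseen review plan sets no different rule. Second, and without any such assumption, the SAP contains no summary of new organisms in subjects who do not fail clinically, so the overgrowth evaluation named in the protocol has no analysis.

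The size cannot be derived from the documents. The 4 to 20 subjects per arm are an illustration on assumed rates. The primary endpoint, the non-inferiority test and the sample size are untouched, and a bias toward eravacycline is not shown. This is a correction to descriptive reporting, worth making before database lock because the present text can undercount by rule.

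**What to change.** 1. In SAP 3.1.4 item 4, insert the word baseline before pathogens, and reconcile items 4 and 5, for example by having item 5 refer to rules 1 through 4.
2. In SAP 5.7.3.5, state that for superinfection and new infection, organisms on lists 1 and 3 and *Pseudomonas* species count when they meet the specimen and CFU criteria of 3.1.4 (apart from the baseline timing). List 2 organisms stay excluded. Give *Pseudomonas* its own row by arm. List yeast and fungi separately by MRC judgement, since the 3.1.4 thresholds are written for bacterial isolates.
3. Add one descriptive row by arm: subjects with such a new organism at any post-baseline visit regardless of clinical outcome, split by clinical failure (yes/no). List the MIC to the IV drug received; do not split by susceptibility, because SAP 3.1.4 says eravacycline breakpoints have not been set.
4. Align the Microbiological Outcomes Review Plan with this wording.

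The cost is SAP wording and a little programming. Urine cultures at Day 5, EOI, EOT, TOC and FU are already scheduled, and the blinded MRC already reviews post-baseline isolates. No visits, samples or alpha are needed. The downside is that some counted organisms will be colonisers, which the split by clinical failure makes visible.
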